#### **4.2. Participant Exclusion Criteria**

Participants meeting any of the following criteria are not eligible for study participation:

1. Any clinically significant underlying illness in the opinion of the Investigator.
2. Poor venous access.
3. Prior exposure to ARN-75039.
4. History of drug or alcohol abuse within 1 year of Screening in the opinion of the investigator, or a positive test for drugs of abuse or alcohol at Screening or Day -1.
5. Use of any prescription or over-the-counter (OTC) medications, including food supplements, vitamins, herbal medications (e.g., St. John's wort), and cannabis, with the exception of contraceptive medications and as needed (prn) acetaminophen or paracetamol (not exceeding 2 grams/day) within 7 days prior to study drug administration and through the Day 15 Discharge visit.
6. Any female who is pregnant or breastfeeding, or any female who is planning to become pregnant during the study and safety follow-up period.
7. Currently enrolled in another investigational device or drug study, or less than 30 days or 5 half-lives of the prior investigational agent (whichever is longer) or plans to enroll in another investigational device or drug study during the course of this study.
8. Inability to ingest all capsules of a multi-capsule dose within 5 minutes of ingestion of the first capsule.
9. Positive serology for hepatitis B virus (HBV), hepatitis C virus (HCV), or human immunodeficiency virus (HIV) at Screening; participants with adequately treated HCV are eligible for enrollment.
10. Consumption of Seville oranges, grapefruit or grapefruit juice within 72 hours prior to Day 1 or during the study.
11. History of malignancy, except adequately treated basal cell carcinoma or in situ carcinoma of the uterine cervix.

12. Smoking cigarettes, cigars, cigarillos or E-cigarettes
13. Any reason or condition that, in the investigator's opinion, may compromise study participation, present a safety risk to the participant, or may confound the interpretation of the study results.
14. A QT duration corrected for heart rate by Fridericia's formula (QTcF) > 450 millisecond (msec) based on either single or averaged QTcF values of triplicate ECGs obtained over a 3-minute interval (at Screening).
15. Blood product (including plasma) donation within 30 days before Screening.
16. Unwilling to consume a breakfast on study drug administration days.
17. History of:

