2.3 Endpoints

Primary:

- Relative bioavailability comparison of 300 mg neat ARN-75039 in HPMC capsules (Treatment A; reference) to 300 mg ARN-75039 with excipients tablets (Treatment B; comparator) following oral administration under fed conditions.
- PK parameters of 300 mg ARN-75039 with excipients tablets and 300 mg neat ARN-75039 in HPMC capsules, including but not limited to:
 - Area under the plasma concentration-time curve from time zero to time of last quantifiable concentration (AUC_{0-t}).
 - Area under the plasma concentration-time curve from time zero to 24 hours post-dose (AUC_{0-24}).
 - Area under plasma concentration-time curve from time zero to infinity ($AUC_{0-\infty}$).
 - Maximum observed plasma concentration (C_{max}).

- Minimum observed plasma concentration from time zero to 24 hours post-dose $C_{min0-24}$.
- Time to reach C_{max} (t_{max}).
- Half-life ($t_{1/2}$).
- Apparent clearance after extravascular administration (CL/F).
- Apparent volume of distribution during the terminal phase after extravascular administration (V_z/F).

Secondary:

- Type and frequency of treatment-emergent adverse events (TEAEs).
- Type and frequency of treatment-emergent serious adverse events (TESAEs).
- Type and frequency of study drug-related >Grade 1 TEAEs.
- Type and frequency of changes in clinical laboratory values, ECGs, colonic transit time (biomarker), physical examinations, and vital signs.

3 Study Design and Methods

ARN-75039-103 is a comparative, randomized, single-dose, crossover study to assess the PK, safety, and tolerability of neat ARN-75039 in hydroxypropyl methylcellulose (HPMC) capsules against ARN-75039 with excipients in tablet form administered by the oral route in healthy adult participants. The safety assessments will include assessments of vital signs, clinical laboratory values, and ECGs.

A total of 16 participants were randomized 1:1 into one of the following two sequences:

Sequence 1:

[figure not shown]
- Period 1: 300 mg neat ARN-75039 in HPMC capsules (Treatment A; reference product)
- Period 2: 300 mg ARN-75039 with excipients in tablet form (Treatment B; comparator)

Sequence 2:

- Period 1: 300 mg ARN-75039 with excipients in tablet form (Treatment B; comparator)
- Period 2: 300 mg neat ARN-75039 in HPMC capsules (Treatment A; reference product)

A study scheme is provided below:

Sequence 1

Sequence 2

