Written informed consent for study participation will be obtained before any study-related procedures or assessments are performed. All potential participants will be screened for potential participation, and those meeting all eligibility criteria will be offered participation in the study.

Participants will be admitted to the study site on the morning of Day -1, randomized to sequence of study drug administration on Day 1, and will remain on site until study completion at Day 15. Participants will receive the randomized study drug in the morning following a standardized meal. Participants will be dosed on Day 1 and Day 8 with a 7-day wash out period between the two dosing days. Pharmacokinetic (PK) assessments will be performed according to the Schedule of Assessments (SOA) ([Table 1](#)).

Table 1: Schedule of Assessments

Procedure	Period	Screening Period	Admission	Period 1						Period 2								End of Active Treatment		Follow Up Phone Call
	Visit	Screening	P1D-1	P1D1	P1D2	P1D3	P1D4	P1D5	P1D6	P2D-1	P2D1	P2D2	P2D3	P2D4	P2D5	P2D6	P2D7	Discharge	ET	Day 36 +/- 2 days
	Study Day	Days -21 to -1	-1	1	2	3	4	5	6	7	8	9	10	11	12	13	14	15	ET ^a	
Informed consent		X																		
Eligibility criteria review		X	X																	
Randomization				X																
Demographics ^b		X																		
Medical and surgical histories		X	X																	
Vital signs ^c		X	X	X	X	X	X	X	X	X	X	X	X	X	X	X	X	X	X	
Physical examination ^d		X			X							X						X	X	
Pregnancy test ^e		X	X															X	X	
Concomitant medications		X	X															X	X	
Adverse events				X	X	X	X	X	X	X	X	X	X	X	X	X	X	X	X	X

Procedure	Period	Screening Period	Admission	Period 1						Period 2								End of Active Treatment		Follow Up Phone Call
	Visit	Screening	P1D-1	P1D1	P1D2	P1D3	P1D4	P1D5	P1D6	P2D-1	P2D1	P2D2	P2D3	P2D4	P2D5	P2D6	P2D7	Discharge	ET	Day 36 +/- 2 days
	Study Day	Days -21 to -1	-1	1	2	3	4	5	6	7	8	9	10	11	12	13	14	15	ET ^a	
12-lead ECG ^f		X	X	X	X	X	X			X	X	X	X	X				X	X	
Hematology ^g		X	X		X					X		X						X	X	
Drug test (urine) alcohol test (breath)		X	X																	
Serology ^h		X																		
Serum chemistry and coagulation ^g		X	X		X					X		X						X	X	
Urinalysis ^g		X			X							X						X	X	
Admission to site			X																	
Study drug administration				X							X									
PK (plasma) ⁱ				X	X	X	X	X	X	X	X	X	X	X	X	X	X	X	X	
Discharge from site																		X	X	

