- ^f Triplicate ECGs will be performed at screening, admission, dosing Day 1 in each period, and end of treatment (discharge or early termination). Triplicate ECGs will be measured at pre-dose (within -90min), and post dose 1hr (± 20 min), 3hr (± 20 min), 6hr (± 20 min), 8hr (± 20 min), 24 hr (± 60 min), 48 hr (± 60 min), and 72 hr (± 60 min) post dose (for both doses) triplicates measurement will be taken within 5 minutes apart. Subjects should be at rest for 10 minutes prior to ECG. For participants that withdraw or are terminated early from the study, ECG will be performed at the ET visit.
- ^g Samples must be collected following a minimum 8 hours fast.
- ^h Serology includes HbsAg, anti-HCV Ab, and anti-HIV Ab.
- ⁱ PK assessments should be performed on Day 1 of Periods 1 and 2 Pre-dose (hour 0) (within 60 mins prior to dosing), 0.5 hour (± 2 mins), 1 hour (± 5 mins), 2 hours (± 5 mins), 3 hours (± 10 mins), 4 hours (± 10 mins), 6 hours (± 10 mins), 8 hours (± 10 mins), 10 hours (± 10 mins), 12 hours (± 10 mins), 24 hours (± 60 mins), 48 hours (± 60 mins), 72 (± 60 mins), 96 (± 60 mins), 120 (± 60 mins), 144 (± 60 min), and 168 hours (± 60 mins) relative to morning dose and at Discharge or ET visit at approximately the same time (± 1 hr) as the dose of study drug administration. The 168-hour post-dose PID1 may be combined with the pre-dose PK collection for P2D1. P2D7 PK will be collected 144 (± 60 min).

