4.6 Pharmacokinetic Analysis

Pharmacokinetic analyses will be performed for each participant in the PK population. Blood samples will be collected and resulting plasma analyzed to obtain plasma concentrations. The plasma concentration data will be listed at actual and nominal time points by participant. Plasma concentrations will be summarized by treatment at each nominal time point of plasma collection using descriptive statistics (n, mean, SD, CV%, geometric mean, geometric CV%, median, min, and max values), and listed by participant, treatment, sequence and with both nominal and actual plasma collection point.

For plasma concentration data, all values below the quantification limit (BQL) will be labeled as such in the concentration listings and treated as zero for the concentration data summary statistics and mean summary figures.

For PK parameter calculations, concentrations BQL will be set to zero if they occur prior to the first quantifiable concentration and after the last quantifiable concentration. The BQL values in between measurable plasma concentrations will be set to missing.

The plasma PK parameters for ARN-75039 will be estimated by non-compartmental analysis (NCA) methods using Phoenix WinNonlin (version 8.1 or higher, Certara USA Inc., Princeton, NJ, USA) and will be based on actual individual time since dosing of blood sample collection.

The following PK parameters will be computed at minimum from plasma concentration data:

C_{\max}	maximum plasma concentration
$C_{\min 0-24}$	observed plasma concentration from time zero to 24 hours post-dose
t_{\max}	time of maximum plasma concentration
$\lambda_z (k_{el})$	terminal-phase rate constant
$t_{1/2}$	elimination half-life
AUC_{0-24}	area under the plasma concentration-time curve from time zero to 24 hours post-dosing
AUC_{0-t}	area under the plasma concentration-time curve from time zero to time t (time of last quantifiable plasma concentration)

$AUC_{0-\infty}$	area under the plasma concentration-time curve from time zero to infinity
CL/F	apparent clearance
MRT	mean residence time
V_z/F	apparent volume of distribution

The C_{max} and t_{max} will be obtained directly from the experimental observations and AUC_{0-t} will be estimated using the Linear up – Log down trapezoidal method from time 0 hour to last observed concentration hour.

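### Cmin0-24, a listed primary PK endpoint, is defined so that, read literally, it picks up the pre-dose sample and not the 24 h trough

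*SAP*

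**What the plan says.** SAP 2.3 lists Cmin0-24 among the primary endpoints as "Minimum observed plasma concentration from time zero to 24 hours post-dose". The protocol synopsis and Protocol section 2 use the same words.

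The other rules that decide its value are these:

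- **Sampling (SAP Table 1, footnote i):** "PK assessments should be performed on Day 1 of Periods 1 and 2 Pre-dose (hour 0) (within 60 mins prior to dosing"; post-dose draws follow at 0.5, 1, 2, 3, 4, 6, 8, 10, 12 and 24 h and then daily to 168 h.
- **Shared draw (same footnote):** "The 168-hour post-dose PID1 may be combined with the pre-dose PK collection for P2D1".
- **Dosing interval (SAP section 3):** "Participants will be dosed on Day 1 and Day 8 with a 7-day wash out period between the two dosing days".
- **BQL handling for PK parameters (SAP 4.6):** "concentrations BQL will be set to zero if they occur prior to the first quantifiable concentration".
- **Eligibility (Protocol 4.2, criterion 3):** the excluded condition is "Prior exposure to ARN-75039".
- **Carry-over (SAP 4.1):** data are left out of the concentration and PK summaries when the pre-dose value exceeds 5% of that participant's Cmax in the same period.
- **Summaries (SAP 4.6):** every PK parameter except tmax gets a geometric mean and a geometric CV%.

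The parameter is not described consistently. SAP 4.6 gives it as "observed plasma concentration from time zero to 24 hours post-dose", without the word minimum. Protocol section 2 prints the symbol as Cmax0-24. Protocol 7.9 omits the parameter. Neither document gives a derivation rule saying which samples count.

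**The concern.** After a single oral dose the concentration rises from its pre-dose level and then falls. A minimum taken over a window that starts at time zero will usually sit at the start of the profile, before the formulation has had time to act. A 24 h trough is the low point at the end of the interval. The dog PK tables in the protocol report a non-zero 24 h value under the label Cmin 24 hr, so the end of the interval is probably what was intended.

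At stake is one named primary endpoint, which Amendment 3.0 added specifically to improve the PK analysis. Computed as written, it would be tabulated by formulation while saying nothing about the formulation in that column. An analyst who quietly used the 24 h value instead would be making an undocumented choice on a primary endpoint.

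**Working it through.** The plan gives no numerical figure for Cmin0-24 to reproduce. The check applies its rules in order and then tests them on simple profiles.

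**Period 1, literal reading.** The hour 0 sample is inside the window. The participant has never taken the drug, so the sample is BQL and is set to 0. The minimum is 0 for tablet and capsule alike.

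**Count of zeros.** Sixteen participants randomized 1:1 give 8 per sequence. Each formulation is therefore given in Period 1 to 8 participants. If all complete, 8 of 16 values per formulation (16 of 32 overall) are zero. The geometric mean is exp(mean of ln x). Because ln 0 is undefined, neither it nor the geometric CV% can be computed in the usual way.

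**Period 2, literal reading.** The hour 0 sample is taken 168 h after the other formulation. Assuming mono-exponential decline, the residue as a fraction of the initial level is 2^(−168/t½):

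| Assumed t½ (h) | 2^(−168/t½) |
|---|---|
| 12 | 0.006% |
| 20 | 0.30% |
| 30 | 2.1% |
| 48 | 8.8% |

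The documents give no human half-life; Protocol 3.2 only calls it long. The dog values of clearance and Vd in Protocol Table 2 imply t½ = ln 2 × Vd/CL:

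- capsule: 0.693 × 4000/(4 × 60) = 11.6 h
- prototype 1 tablet: 0.693 × 7000/(4 × 60) = 20.2 h

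The residue reaches 5% when 2^(−168/t½) = 0.05, that is at t½ = 168/log2(20) ≈ 39 h. Roughly, below that half-life the Period 2 value is zero or a small residue that stays in the summaries. Above it, the 5% rule removes Period 2 and only the Period 1 zeros remain.

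**Simulated profiles.** The assumptions are a one-compartment oral model, ka 0.6/h, half-life 8 to 72 h, absorption lag 0 or 0.75 h, tablet exposure set at 1.25 times capsule, and the residue of the earlier dose added.

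- Period 1: Cmin0-24 is 0 for both formulations in every scenario.
- Period 2, no lag: the minimum is always the hour 0 sample. With the lag it is the 0.5 h sample, which then contains only the earlier formulation's residue.
- The 24 h sample is never the minimum.
- The Period 2 tablet/capsule ratio is 0.80 (1/1.25), the inverse of the true 1.25, because each value measures the other product.
- Taking the 24 h concentration instead returns 1.25 in Period 1 at every half-life.

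**Alternative reading: pre-dose draw counted as before time zero.** The Period 1 capsule profile in the same model is C(t) = 100 × ka/(ka − k) × (e^(−kt) − e^(−ka·t)), with k = ln 2/t½. Without lag:

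| t½ (h) | C at 0.5 h | C at 24 h | Lowest post-dose sample |
|---|---|---|---|
| 8 | 25.3 | 14.6 | 24 h |
| 12 | 25.5 | 27.7 | 0.5 h |
| 20 | 25.7 | 46.2 | 0.5 h |
| 30 | 25.8 | 59.7 | 0.5 h |

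The 0.5 h sample is also lowest at 48 and 72 h. With a 0.75 h lag the 0.5 h value is 0 at every half-life. On this reading the endpoint coincides with the trough only when elimination is fast and absorption prompt.

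**The case against.** Five points can be made for the plan.

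1. **The pre-dose draw may fall outside the window.** PK parameters use actual times, and that draw precedes dosing by up to 60 minutes. This is a fair reading, and it means the Period 1 zeros are not certain. But the schedule labels the draw hour 0, nothing excludes it, and the alternative usually swaps a pre-dose value for an absorption-phase one.
2. **The trough is still reported.** This stands. SAP 4.6 summarises concentrations by treatment at each nominal time, including 24 h. A reader might infer that the 24 h level is never compared between formulations. It is compared descriptively; what is missing is a correctly defined parameter.
3. **No decision uses Cmin0-24.** This also stands. SAP 4.6 limits the 90% CI and the 80.00–125.00% limits to Cmax, AUC0-t and AUC0-∞. Other primary parameters, such as t½ and CL/F, are likewise not modelled, so the absence of Cmin0-24 or AUC0-24 from the ANOVA is not in itself a fault.
4. **The Period 2 error cannot be sized.** A reader might assume a 48 h half-life and infer reported values about 8-fold below the 24 h level (2^(−24/48)/2^(−168/48) = 0.707/0.088 ≈ 8). The documents do not support that. At 48 h the simulated pre-dose/Cmax is 7–11%, so the 5% rule would remove those values from the summaries. At much shorter half-lives the residue may be BQL.
5. **The labelling slips are typographical.** Probably so: the synopsis and the SAP glossary give the full definition. But the full definition is the one that causes the problem.

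**Conclusion.** The concern holds for the definition as written. Under the literal reading, Cmin0-24 is 0 for both formulations in Period 1. In Period 2 it is zero or the other formulation's 168 h residue, summarised only when that residue is 5% or less of the period's Cmax. Under the actual-time reading it tends to be an early absorption sample. Neither reading reliably gives a trough, and any zeros make the planned geometric statistics unusable.

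The Period 1 result rests on the hour 0 label and on participants being drug-naive. The count of 16 zeros in 32 values also needs all 16 participants to complete both periods. The Period 2 and 0.5 h results depend on assumed half-life and absorption, since neither a human half-life nor a quantification limit is given.

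The consequence is limited to one descriptive primary endpoint. The formal relative bioavailability conclusion is untouched. This should be fixed, but it does not threaten the main comparison.

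**What to change.** In the protocol synopsis, Protocol sections 2 and 7.9, and SAP 2.3 and 4.6, replace Cmin0-24 with C24: the observed plasma concentration at the nominal 24 h post-dose sample. State that pre-dose and absorption-phase samples do not enter it, and that the existing 5% carry-over rule applies. This matches the quantity in the dog tables. If the Cmin0-24 name is kept for continuity, the same definition should sit under it, with the Cmax0-24 symbol in Protocol section 2 and the incomplete description in SAP 4.6 corrected.

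Optionally, report the tablet/capsule ratio of geometric means for C24 with a 90% CI from the mixed model already planned, labelled descriptive and outside the 80.00–125.00% decision. Adding AUC0-24 to the model is a matter of preference and is not needed here.

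The cost is a short protocol clarification, matching SAP and table-shell wording, and at most one extra model run. The 24 h sample is already scheduled in both periods.

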3.1 Study Assessments

3.1.1 Pharmacokinetic Assessments

The primary pharmacokinetic assessments are based on ARN-75039 plasma concentrations.

Fifteen venous blood samples will be withdrawn via an indwelling cannula or by venipuncture at regular time intervals. The exact date and time of PK sample collection is to be documented in eCRF. Blood samples will be collected prior to and following administration of the single oral dose of neat ARN-75039 in HPMC capsules or ARN-75039 with excipients in tablet form at according to the timepoints listed in the SOA (Table 1).

The actual sampling time will be used for estimating PK parameters.

3.1.2 Safety Assessments

Safety assessments include the incidence of treatment emergent events (TEAE); study completion and discontinuation information; vital signs; height, weight, and body mass index (BMI), and physical examination (PE); clinical laboratory values, and ECG. Medical observations, and adverse events reporting will be recorded by clinic staff throughout the study. Any safety assessment may be repeated at the discretion of the Investigator.

3.2 Randomization

To eliminate potential bias, participants will be randomly assigned to either Sequence 1 or Sequence 2. The study site will utilize the randomization result generated to administer the appropriate study drug formulation to participants in accordance with the Study Schema.

A randomization schedule was generated programmatically by the statistician prior to the start of the study, displaying subject assignments to each sequence with a unique Subject Identification Number. Eligible participants will be preassigned an Identification Number sequentially according to the time of arrival at admission to the clinical research unit (CRU). Once subject eligibility is confirmed, the Identification Number is assigned and may not be re-used. The date and time of the dosing will be recorded in the electronic case report form eCRF.

Participants who are unable to complete the sequence may be replaced and/or additional participants may be included at the discretion of the Sponsor. Replacement participants will be assigned to the same sequence as the participant who did not complete the study but will be assigned a new Identification Number.

3.3 Sample Size Justification

The sample size of 16 evaluable participants proposed for this study was not based on statistical analysis assessments but was judged to provide a sufficient dataset to be able to make direct comparisons in pharmacokinetic parameter estimates between the reference

and test groups in this clinical study. Participants withdrawn due to a study drug-related Grade >1 TEAE will not be replaced. Participants who are withdrawn due to a study drug-related Grade 1 TEAE may be replaced. Participants who are withdrawn due to a reason other than a drug-related TEAE during the Treatment Period may be replaced as necessary to obtain 16 evaluable participants at the end of the clinical study.

3.4 Data Handling

Summaries for continuous variables will include the descriptive statistics for number of participants (n), mean (arithmetic and geometric), standard deviation (SD), coefficient of variation (%), minimum (min), median, and maximum (max). Summaries for categorical (discrete) variables will include the number and/or percentage of participants in a specific category.

Conventions for presentation of numerical data in safety outputs (data collected in eCRF) are as follows:

- Minimum and maximum values will be presented to the same number of decimal places as (eCRF) data.
- Means and medians will be presented to one more decimal place than the eCRF data. Standard deviations will be presented to two more decimal places than the eCRF data.

For Plasma concentrations and PK parameters summary tables, if sample size n is ≥ 2 , then a value will be presented for a statistic in the summary tables but if n is less than 2 (n=1), then a dash will be used in place of the value.

Plasma concentrations and PK parameters in tables and listings will be displayed with 3 significant figures as follows:

- Values ≥ 0.0001 and < 1 will be reported with 3 significant figures (e.g., 0.0123).
- Values ≥ 1 and < 10 will be reported with 3 significant figures (e.g., 1.02).
- Values ≥ 10 and < 100 will be reported with 3 significant figures (e.g., 10.2).
- Values ≥ 100 and < 1000 will be reported with 3 significant figures (e.g., 102).
- Values ≥ 1000 will be reported with 3 significant figures (e.g., 1020).
- Values = 0 will be reported as 0 (applies only for listing)
- Values for t_{\max} will be reported using one decimal place (2 significant figures).

For Safety Endpoints:

Baseline is defined as the last value measured prior to the first dose of study drug for each period. For safety parameters that are measured during each study period, the baseline is defined as the value prior to the first dose of each period.

Change from Baseline is defined as [Post-baseline Value – Baseline Value].

4 Data Analysis

